An optimal surgical environment proves to have a beneficial effect on the healing of the anastomosis. For instance, anesthesia could possibly reveal shared risk factors in relation to anastomotic healing, perfusion and ischemia. Other changes in hemodynamic parameters during surgery can also be related to the risk of CAL. The importance of individual perioperative hemodynamic parameters during surgery on the postoperative outcome is widely described in literature. This warrants the hypothesis that optimal perioperative hemodynamic parameters are relevant on the healing of an anastomosis. Studies show that a large number of parameters are out of balance during the operation. For example, the influence of an elevated glucose in non-diabetes patients or intraoperative hypotension has been associated with a higher risk for postoperative adverse events. A lot of risk factors for CAL are not taken into account yet, even though there is plenty of information available that suggests further research concerning these parameters. Modifiable factors that are able to be optimized. These parameters are not currently being explicitly monitored or optimized during the operation, in particular, while making the anastomosis. Additionally, optimal values for hemodynamic parameters are even hardly established.

Due to these modifiable factors more studies are gaining interest in a multidisciplinary approach to prevent surgical complications. Since CAL has a multifactorial etiology, it can be hypothesized that intervention in modifiable risk factors might lead to a reduction of the incidence of CAL. This suggests a close collaboration of the surgical and anesthesiological team is essential, making this the first attempt to construct a tool that could reduce the patients' risk of CAL intraoperatively.

Prior to this multicenter prospective cohort study, a systematic review was performed summarizing the preceding studies on (perioperative) risk factors. The summary contains a report of these parameters, how important they are and if they show deviations during surgery. It was used to compose the checklist for the Leakage Check procedure, providing guidance on the available knowledge on this topic.

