Statistics are used to calculate a possible difference between patient outcomes and deviations in perioperative parameters, by means of a chi-squared test. The patients are divided into two groups, with and without CAL complication. The final purpose of this study is to optimize the risk factors in a follow up study. The determined perioperative risk factors will be ascribed optimum values by using the results of the Leak Check-Study. Dividing the patients into leaking and non-leaking groups to determine the most average values for perioperative factors. These results can be compared with the so-called optimal values from the literature of the systematic review. From these results, a new Leakage Check questionnaire will be designed for in the follow up study, containing often aberrant and modifiable perioperative factors and their optimal range. It depends on the obtained results how the optimization will take place.

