**Table 2. Leakage Check procedure**

General condition	Perfusion	Contamination and visibility	Surgery related factors
Temperature	Blood loss		Analgesia
Glucose	O 2 saturation	Contamination surgical field	Surgeon Fit to perform
Antibiotics	MAP		Elective operation Anastomose
Inotropic	Subjective rate of local perfusion		Operation Intra operative event\
Door movements	Fluid balance		Stoma Hospital

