## **6. STATISTICAL ANALYSIS**

### **6.1 Statistical plan**

Evaluation of relationships between parameters deviations and leakage rates of anastomosis. Analyses for outcome will be performed on the 2 groups, one with CAL and a group without CAL. Data will be analyzed with Statistical Package for the Social Sciences software version 20 (SPSS Inc., Chicago, IK, USA).

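### Average values in leaking and non-leaking patients cannot supply the optimum values or optimal range planned for the follow-up checklist

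*Protocol*

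**What the plan says.** Section 3 (Study design) of the protocol states the aim: "The determined perioperative risk factors will be ascribed optimum values by using the results of the Leak Check-Study". The next sentence gives the method: "Dividing the patients into leaking and non-leaking groups to determine the most average values for perioperative factors". A literature check follows: "These results can be compared with the so-called optimal values from the literature of the systematic review". The product is a new questionnaire for the follow-up study, "containing often aberrant and modifiable perioperative factors and their optimal range". The paragraph ends by leaving the manner of optimisation open until the results are known.

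The only test named in section 3 relates outcome to parameter deviations "by means of a chi-squared test". Section 6.1 adds: "Analyses for outcome will be performed on the 2 groups, one with CAL and a group without CAL". Neither section names a model of leak risk across the values of a parameter. Section 1 concedes that "optimal values for hemodynamic parameters are even hardly established". Section 2 (Study aim) describes the follow-up study as the ultimate goal.

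**The concern.** An optimum is the value, or range of values, at which leak risk is lowest. Finding it requires risk as a function of the parameter. The protocol proposes the reverse: the average of the parameter given the outcome. When leakage is uncommon, the average among non-leakers mostly describes what patients in the cohort usually have, and says little about where risk is lowest. An average is also a single point, whereas the stated product is a range.

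At stake are the values carried into the follow-up checklist, where factors are to be optimised. If they come from this rule, they will tend to restate current practice as the optimum.

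**Working it through.** The protocol gives no figure on this point to reproduce. Inputs from the document: leak incidence 8-13% (section 1) and about 2000 patients (sections 4.1 and 4.4). Assumptions: a standard-normal parameter, a logistic leak risk, and the risk shapes and slopes below. The protocol does not say that risk is two-sided for any item, including "Fluid balance".

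**Step 1. Position of the non-leaker average (any risk shape).** With leak rate π,

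mean(all) = π × mean(leakers) + (1 − π) × mean(non-leakers),

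so mean(non-leakers) − mean(all) = −π × [mean(leakers) − mean(non-leakers)].

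| Difference between groups | Shift at π = 0.08 | Shift at π = 0.13 |
|---|---|---|
| 0.25 SD | 0.02 SD | 0.03 SD |
| 0.5 SD | 0.04 SD | 0.065 SD |
| 1 SD | 0.08 SD | 0.13 SD |

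**Step 2. Comparison with the true lowest-risk value.** Simulation of 2,000,000 patients, calibrated to each leak rate:

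| Assumed logit risk | Leak rate | Non-leaker mean | Leaker mean | Risk at non-leaker mean | Comparison risk |
|---|---|---|---|---|---|
| Centred U, 0.5x² | 8% | 0.00 | 0.00 | 4.0% | 4.0% at the minimum (0) |
| Centred U, 0.5x² | 13% | 0.00 | 0.00 | 7.1% | 7.1% at the minimum (0) |
| Off-centre U, 0.5(x − 1)² | 8% | +0.10 | −1.19 | 2.5% | 1.7% at the minimum (+1 SD) |
| Off-centre U, 0.5(x − 1)² | 13% | +0.15 | −0.99 | 4.8% | 3.4% at the minimum (+1 SD) |
| Linear, OR 2 per SD | 8% | −0.05 | +0.61 | 6.5% | 1.8% at −2 SD |
| Linear, OR 2 per SD | 13% | −0.08 | +0.57 | 10.6% | 3.1% at −2 SD |

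The off-centre row agrees with step 1: 0.08 × (0.10 + 1.19) = 0.10. At 13% the shift is 0.15, above the 0.13 in the first table, because the groups there differ by more than one SD: 0.13 × (0.15 + 0.99) = 0.15.

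**Step 3. What the averages show.**
- *Centred U at 8%.* The averages are equal, although risk rises from 4.0% at the centre to about 24% at ±2 SD (odds 0.0401/0.9599 = 0.0418; × e² = 0.309; 0.309/1.309 = 0.236). Only the spread differs: SD 1.58 in leakers, 0.93 in non-leakers.
- *Off-centre U.* Leakers average low and non-leakers near zero, which reads as low values being bad. The averages show neither the minimum at +1 SD nor the rise beyond it.
- *Linear.* The non-leaker average sits almost at the overall mean, while risk keeps falling in one direction.

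**Step 4. A range built from non-leakers.** The protocol does not say how the range would be formed. If it were the non-leaker mean ± 2 SD, the centred U at 8% would give ±1.86 SD. Risk at that edge is about 19% (0.0418 × e^(0.5 × 1.86²) = 0.236; 0.236/1.236 = 0.19), more than twice the average risk.

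**The case against.** **The rule is looser than a formula.** The sentence is a fragment. A literature comparison follows it, and the manner of optimisation is left open. That softens the consequence, but the comparison is optional and has no decision rule, and section 1 says optimal values are hardly established. Leaving open how factors will later be optimised does not replace the method for finding the values.

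**Both groups are examined.** This stands in part. The leaker average can differ clearly, so it would be too strong to infer that the method merely returns the population mean; that describes the non-leaker average, and only approximately. It would also be too strong to infer that every U-shaped risk is missed. The averages are blind only to a U centred on the mean, and there the average happens to coincide with the lowest-risk value. A chi-squared test on deviations could still detect such a U if deviation were defined in both directions.

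**The linear case has no interior optimum.** True. It shows that the average is uninformative about the direction of lower risk; it does not show a missed minimum. In the off-centre case the excess risk at the averaged value is moderate: 2.5% against 1.7% at 8% leakage.

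**Data-derived thresholds.** A reader might infer that cut-points for deviation will be searched for in these data and then tested on them, inflating false positives. The protocol plans no such search. Thresholds could come from the systematic review, and a statistical analysis plan, not shown here, may list them. Any loss of power from dichotomising for the chi-squared test is a separate matter.

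**Place in the study.** Optimum values are not among the objectives in section 2 or the parameters in sections 5.1.1 and 5.1.2, and the study is observational. This stands and limits the severity.

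**Conclusion.** The point holds in this limited form. The stated method does not identify a low-risk value or range. The algebra in step 1 needs no assumption about risk shape: at 8-13% leakage the non-leaker average is within 0.08-0.13 SD of the overall mean for a one-SD difference between groups, and closer for smaller differences. The illustrations of what is lost (no signal for a centred U, and a minimum at +1 SD estimated at +0.10 to +0.15 SD) rest on assumed shapes and slopes.

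The documents do not support saying that the rule always gives a wrong target, since with a centred U it lands on the minimum by coincidence. The wording should be corrected before analysis. The primary objective of identifying risk factors does not rest on this sentence, and the derived values take effect only in the follow-up study.

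**What to change.** Replace the averaging sentence in section 3 with wording to this effect: for each main continuous checklist parameter recorded as a number, leak risk will be modelled by logistic regression with a 3-knot restricted cubic spline; predicted risk will be shown over the observed range with 95% confidence intervals; the lowest-risk range will be reported with bootstrap uncertainty, as hypothesis-generating for the follow-up study. Where a yes/no label for deviation is used, fix its threshold and record its source before outcomes are analysed.

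Keep the model within the available events. At 8% of 2000 there are about 160 leaks. Table 2 has roughly seven items that look continuous (temperature, glucose, door movements, blood loss, oxygen saturation, MAP, fluid balance). At 2 degrees of freedom each that is 14, or about 11 leaks per degree of freedom (160/14) before any adjustment. Restrict the splines to a few main items chosen in advance, or use penalisation.

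Cost: a change of wording and modest programming. It requires numeric values to be stored, which should be confirmed because Table 2 lists item names only. Flat curves may support only a wide range, which would then be the correct result to carry forward.

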### **Processing of data**

There is data collected from three different time periods:

- Preoperative data classification into complication risk.
- Leak Check data intraoperatively.
- Postoperative outcome data.

Participating health centers are offered two methods of processing the data.

## 4. STUDY POPULATION

### 4.1 Population

The intended population for this study consists of all consecutive adult patients undergoing colorectal surgery with anastomosis for benign as well as malign cause and treated at the participating centers.

The intended population for this study consists of 2000 adult patients undergoing colorectal surgery with anastomosis for benign as well as malign cause.

### 4.2 Inclusion criteria

Subjects participating in this exploratory scientific project must meet all of the following criteria:

- Subjects undergoing colorectal surgery with any kind of anastomosis.
- Can speak and understand the Dutch language.
- Is pre-operatively in good physical health as defined by ASA (American Society of Anaesthesiologists) physical status classification system 1, 2 and 3.
- Is capable of giving informed consent.

### 4.3 Exclusion criteria

- No exclusion criteria.

### 4.4 Sample size calculation

In order to ensure there will be enough patients to properly evaluate the effect of optimizing perioperative risk factors on the incidence of CAL, we performed a power analysis. This sample size was calculated using a 2-sample test of proportions with the two primary subgroups being patients with de deviating perioperative parameters and patients without deviating perioperative parameters. Calculation of an initial sample size of >2000 patients, assuming a significance level of  $\alpha = 0,05$ , to achieve a power of 80% to detect a difference of  $\delta = 0,06$  between the subgroups, assuming a 8% leak in the group with deviating risk factors and 2% in the group without deviating risk factors.

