Colorectal anastomotic leakage is an important topic in scientific research due to the severe consequences. A number of anastomotic studies resulted in a decline of leakage. Nevertheless, CAL remains a surgeons most feared complication with an incidence varying from 8-13%. Main research focus has been directed towards optimization of surgical techniques and determining relevant risk factors. Several studies put a lot of effort in using different materials wrapped around the connection area to prevent leakage. These have not been fully successful until now. Researchers are now aiming at early detection of CAL to intervene as quickly as possible, however prevention is preferred above early detection. Many of these factors, i.e. age and sex, can be identified preoperatively. Some of them have been included in a colon leakage score (CLS) to determine in advance whether an anastomosis or stoma should be constructed. The CLS is a list of risk factors derived from a systematic search that is pre-checked before all colorectal surgeries. It contains preoperative risk factors each with a value and predicts by means of a total score the CAL-risk. The only downside to this is that after determining a high CAL-risk, there is no possibility to change or improve the risk factors. There are pre-habilitation programs that improve the patient's preoperative status, focusing on the risk factors related to the patients' lifestyle. Sadly the effect on reducing the risk is very disappointing. There is a great deal of knowledge about risk factors, but because they are

largely non-modifiable they can only make a prediction and not help with the reduction of the leakage risk.

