### 5.1.2 Secondary study parameters

Secondary parameters are number of deviating risk factors in total and feasibility of scoring a checklist during surgery.

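### The 8% and 2% leak rates behind the power calculation cannot be reconciled with the protocol's own 8-13% incidence, and the expected share of patients deviating is not stated

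*Protocol*

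**What the plan says.** Section 4.4 describes the calculation as follows: "This sample size was calculated using a 2-sample test of proportions", the two groups being "two primary subgroups being patients with de deviating perioperative parameters and patients without deviating perioperative parameters". The rates are given as "assuming a 8% leak in the group with deviating risk factors and 2% in the group without deviating risk factors". The significance level is 0.05, with sidedness not stated, and the aim is "to achieve a power of 80% to detect a difference" of 0.06. The result reads "Calculation of an initial sample size of >2000 patients". The section gives no cut-off, no minimum number of deviations and no expected size for either group.

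On the overall leak rate, section 1 says "CAL remains a surgeons most feared complication with an incidence varying from 8-13" per cent, and the Summary gives the same range. On how often parameters deviate, section 1 says only this: "Studies show that a large number of parameters are out of balance during the operation". It gives no percentage.

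The analysis is described differently from the powered contrast. Sections 3 and 6.1 divide patients into those with and without leakage and relate leakage to deviations in the parameters; section 3 names a chi-squared test. Section 5.1.2 adds a count: "Secondary parameters are number of deviating risk factors in total".

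**The concern.** The two subgroups in section 4.4 are complementary: every patient is in one or the other. The overall leak rate must therefore be a weighted average of 8% and 2%. The protocol's incidence range starts where that average can at most end, so the rates used for planning and the rate used as the rationale do not describe the same population.

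The missing share of patients deviating adds to the problem. A two-group comparison is driven by its smaller group, and with many parameters on the checklist the reference group might be large or very small. Without the share, a reader cannot tell whether 2000 patients give ample power or very little. The powered contrast also pools all parameters, whereas the primary objective is to identify individual modifiable factors.

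**Working it through.** **Inputs.** From section 4.4: 8% leak with deviation, 2% without, alpha 0.05, power 80%, more than 2000 patients. From the Summary and section 1: overall incidence 8-13%. The share deviating, s, is not given, so it is varied below. A two-sided test is assumed.

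**The plan's own figure.** With equal groups and the pooled normal approximation, 8% versus 2% needs 206 per group, 412 in total (478 with continuity correction; 326 or 390 if one-sided). The stated size of more than 2000 is not reproduced. A two-sided uncorrected total near 2000 appears only with an extreme, unstated split: 2068 if 94% deviate, or 1925 if 4% deviate. Whether the size follows from its inputs is a separate matter. What matters here is that neither split gives an overall rate within 8-13%: the first gives 0.94 x 8% + 0.06 x 2% = 7.6%, the second 0.04 x 8% + 0.96 x 2% = 2.2%.

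**Consistency of the rates.** Overall = 8% x s + 2% x (1 - s) = 2% + 6% x s, so s = (overall - 2%) / 6%.

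| Overall incidence | Implied share deviating |
|---|---|
| 5% | 50% |
| 7.4% | 90% |
| 8% | 100% |
| 10% | 133% (impossible) |
| 13% | 183% (impossible) |

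**What the deviating group's rate would have to be.** Keeping 2% in the reference group, the rate is (overall - 2% x (1 - s)) / s.

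| Overall | 50% deviating | 90% deviating |
|---|---|---|
| 8% | 14% | 8.7% |
| 13% | 24% | 14.2% |

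**Power at 2000 patients as the reference group shrinks.** Power = Φ[(0.06 - 1.96 x SE0) / SE1], with SE0 from the pooled rate and SE1 from the two separate rates. For 120 reference patients and 1880 others, the pooled rate is 0.0764, SE0 = √(0.0764 x 0.9236 x (1/1880 + 1/120)) = 0.0250 and SE1 = √(0.0736/1880 + 0.0196/120) = 0.0142. This gives Φ(0.77) = 78%.

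| Reference group | Expected leaks there at 2% | Power |
|---|---|---|
| 1000 | 20 | >99.9% |
| 200 | 4.0 | 97% |
| 120 | 2.4 | 78% |
| 88 | 1.8 | 57% |
| 40 | 0.8 | 14% |

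With so few expected leaks the normal approximation is rough in the lower rows, but the direction is not in doubt.

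**The case against.** Three stronger readings are tempting, and the documents support none of them.

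First, a reader might infer that the exposure is fixed as any deviation versus none. That is the natural sense of with and without, but the protocol never states it. The exposure in section 4.4 is undefined rather than set as all-or-none.

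Second, a reader might conclude that the reference group will be empty. The identity shows only that the planning figures conflict. The 8-13% is cited from the literature. This cohort is limited to ASA 1-3 (section 4.2), includes benign disease (section 4.1) and counts only leaks requiring reintervention (section 3), so its rate may be lower. At 7.4% overall the same 8% and 2% leave 200 of 2000 patients without deviation and about 97% power. Scenarios built from the checklist do not settle it either. If parameters deviate independently, 11 of them at 10% each leave 2000 x 0.9^11 = 628 patients without deviation and power above 99%, while 19 at 20% each leave 2000 x 0.8^19 = 29 and about 7%. The probabilities and the independence are assumptions, positive correlation would enlarge the reference group, and several items in Table 2 (such as hospital and type of operation) have no evident deviating state.

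Third, a reader might say that the study cannot show which parameters matter. Sections 3 and 6.1 relate parameter deviations to leakage, and section 5.1.2 counts them. As a comparison, the pooled contrast appears only in section 4.4.

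It can also be said that cut-offs are often left to an analysis plan, which is not at hand. That is fair for the analysis. It does not cover two leak rates, already fixed in the protocol, that contradict its stated incidence.

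**Conclusion.** The point holds as a fault in the sample-size inputs. The 8% and 2% rates allow at most 8% overall, and that only if all patients deviate, against a stated 8-13%. This follows from arithmetic on the protocol's own figures and needs no outside assumption beyond the two groups together covering the cohort.

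The unstated share matters because power at 2000 patients runs from above 99.9% with 1000 reference patients to 14% with 40. Those figures assume the 8% and 2% rates, a two-sided 5% test and the normal approximation. The documents do not show where in that range the study lies. The fault is confined to the calculation in section 4.4; the planned analysis of leakage against parameter deviations does not rest on it.

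**What to change.** In section 4.4:

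1. State what counts as deviating for the powered contrast, and the share of patients expected to deviate.
2. Restate the two leak rates so that, weighted by that share, they average to the stated incidence. With 2% in the reference group and 8% overall, for example, the deviating group must leak at 14% if half deviate or about 8.7% if 90% deviate. Alternatively, justify an overall incidence below 8% for this population.
3. Restate the sample size, or the power at 2000 patients, that follows, and say whether the test is one- or two-sided.
4. Because the primary objective concerns individual factors, base the calculation on deviation in a single parameter, or on the number of deviations already listed in section 5.1.2, so that it matches the analysis in sections 3 and 6.1.

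The cost is protocol wording and a recalculation. The same checklist data are used. The restated figures may be less favourable than those now given.
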